#### **12.2 What are the potential benefits of this study to individual participants? (This does not include payments, compensation, or incentives.)**

Primary benefits to participating in this study include exposure to Protective Behavioral Strategies and, for those in the counterfactual condition, a mental tool to help implement these strategies throughout one's everyday life. Some secondary benefits may be experienced: Participation in the study gives participants a first-hand look at research. This "laboratory" experience may help participants obtain a better understanding of psychology research that they may be interested in pursuing in the future, as these are all students currently taking a psychology course at TAMU.

#### **12.3 What are the potential benefits of this study to the population or society?**

The present study aims to increase psychology's understanding of the social-cognitive mechanisms (specifically, counterfactual thinking) that foster intention formation and promotion. By understanding the most salubrious way to think about negative alcohol events, the present study could influence alcohol-use strategies for treating binge-drinking in college students or other health-related issues. Furthermore, we hope to increase psychology's understanding of the effect of counterfactual thinking on other research areas (such as, perceived behavioral control) correlated with behavioral change.

### **13.0 Personally Identifiable Information**

#### **13.1 Indicate which of the following personally identifiable information (PII) will be accessed or recorded in association with this study:**

- None
- Name
- Web addresses (URLs)
- Full Face Photographic Image
- Internet IP Address
- Health Plan Beneficiary Number
- Certificate/ License Number
- Any Other Unique Identifier or Combination
- Geographic Information (including city and ZIP)
- Vehicle Identification Number and Serial Numbers Including License Plate Number
- Telephone Number
- Email address
- Fax number
- Social Security Number
- Medical Record Number
- Account Number
- Medical Device Identifiers
- Biometric Identifiers
- Dates directly related to an individual (including birth, death, admission, discharge, date of procedure)
- Educational Records

Will any PII in your possession be coded?

Yes  No

Will you have the code in your possession?

Yes  No

Is this personally identifiable information considered Protected Health Information (PHI)? (PHI is any of the 18 identifiers listed above collected by or received by a covered entity, which includes a healthcare provider, healthcare clearing house, or as defined in the University SAP 16.99.99.M0.01.)

Yes  No

**\*If Yes, additional requirements may be involved such as HIPAA authorization, Waiver of Authorization, or Data Use Agreement, or other agreements.**

**13.2 Explain why you need to obtain personally identifiable information (list all of the data fields to be collected):**

In order to connect the participants' data from Parts 1-6, we will need some identifier to be used during the data collection process. By using the participants TAMU email, this allows us to connect all parts as well as contact participants on follow-up sessions should they not qualify (i.e., did not follow writing prompt instructions). However, as soon as our study's data collection is complete and Parts 1-6 data are matched in one complete data set, participants' TAMU emails will be changed to randomized Participant ID numbers and will be deleted. Thus, once the data collection is complete, there will be no personal identifying information housed alongside our data.

13.3 Does this study involve use of Protected Health Information (PHI) being received from a Covered Entity (e.g. healthcare provider, healthcare clearing house, health plan)?

Yes  No

Will the provider be a collaborator on this study who will maintain the code to the PHI in their possession?

Yes  No

If yes, identify the covered entity and provide the data use agreement or business associate agreement.

**Covered Entity:**

Does this study involve collection of PHI from participants or receipt of PHI from a covered entity?

Yes  No

Does this study involve distribution of PHI to a Covered Entity (e.g. healthcare provider, healthcare clearing house, health plan)?

Yes  No

If Yes to any of these three previous questions, PHI authorization or a waiver of PHI authorization is required. Is a waiver of PHI authorization being requested? For more information, see the additional information online: <http://rcb.tamu.edu/humansubjects/resources/consentinfo>

Yes  No

Please attach the HIPAA Authorization as needed to the application.

#### 13.4 Will the PHI used in this study be stored with encryption?

Yes  No

How is PHI transmitted electronically being protected?

---

How is PHI data protected?

---

Who has access to PHI?

---

#### 14.0 Retrospective Details (Please note: This refers to the analysis of data, documents, records, or specimens that were existing as of the date of the IRB application.)

##### 14.1 Will existing data or documents be used (e.g., patient records/charts, samples/specimens, public records, surveys, evaluation tools, etc.)? **NOTE: If you answer NO to this question, please skip the remaining questions in this section.**

Yes  No

If Yes, then:

Describe the data or documents that will be used.

What is the date range of the original data collection?

---

How will the existing data be obtained? Additional information may be required to establish authority to use the data previously collected.

##### 14.2 Will your research be limited to only existing data or specimens? **NOTE: If data/specimens will be collected after submission of this application, then the answer here is "No". If you answered NO to this question and the main question above, please skip the remaining questions in this section.**

Yes  No

#### 14.3 Will existing specimens be used (e.g., human blood, tissue, saliva, etc.)?

Yes  No

If Yes, then describe the specimens that will be used and how they will be obtained.

---

Indicate the number of specimens.

---

How will the specimens be obtained?

---

Provide the documentation from the holder of the samples that gives you permission to use the samples for research purposes. If the samples were collected for research purposes, provide a copy of the approved informed consent document used to obtain the samples.

#### 14.4 Retrospective Details – Publicly Available

Is the source of the data for your research accessible by the general public?

Yes  No

Provide the link if applicable.

---

#### 14.5 Retrospective Details – Identity

Will it be possible to determine a subject's identity directly or indirectly through a link (e.g., Medical Record Number (MRN), participant code, IP address, email)?

Yes  No

#### 14.6 Retrospective Details – Waiver of Informed Consent

Is it impractical to obtain informed consent from the subjects?

Yes  No

If Yes, then please complete the Waiver of Informed Consent information in the next section.

#### 14.7 Retrospective Details - Waiver of Document of Informed Consent

Is it possible to obtain informed consent, AND the only link between the data and the human subject would be the signed informed consent document?

Yes  No

### 15.0

### Costs and Compensation

#### 15.1 What are the costs to participants (monetary, time, expense, etc.)? Identify the costs and specify the amount.

The only cost to participants is the amount of time required to complete the study. All parts of the study will be completed online (using Qualtrics survey). Each part can be completed in about 30 minutes time.

#### 15.2 Will participants receive any compensation for participation in the study? Note: For payments to participants, please see University SAP Payment of Survey and Research Participants 21.01.99.M0.03. (<http://rules-saps.tamu.edu/PDFs/21.01.99.M0.03.pdf>)

Yes  No

If Yes, then identify the amount of compensation, method of payment, payment schedule, and justification. If more than a single session with the participant, then the schedule should include incremental payments.

Participants will receive compensation in the form of research credits for their psychology course. Participants will receive 1 credit of research participation after Part 1 (regardless of whether they continue on to Part 2, 3, 4, 5, and 6). Participants will receive additional credits of research participation credit after each additional follow-up they complete (1 credit for each part). This means that participants who complete Parts 1-6 will receive a total of 6 credits. They will receive 1 credit after they complete Part 1 and those who complete Part 2, 3, 4, 5 and 6 will receive the additional 6 credits. For those waves conducted later in the semester, they will receive the number of credits based on the number of sessions they complete (4 weeks = 4 credits; 5 weeks = 5 credits). These credits will be applied using the TAMU SONA online participation system.

#### 15.3 In case of injury, explain who will pay for the treatment. (If not applicable, then note "N/A.") Is there a contract in place - is subject injury covered by an outside entity?

N/A

**15.4**

**What extra costs will be incurred by third-party payers because of subjects' participation?**

No costs will be incurred by third-party payers because of subjects' participation.

**16.0****Recruitment****16.1 How will potential subjects be identified? (How do you know who to contact to participate in the study?)**

Potential subjects will be recruited by the TAMU online participation pool system, SONA. Participants will sign up for Part 1 and either complete part 1 in the lab or receive a link to the qualtrics survey online. Once they complete Part 1, they will be allowed to participate in Part 2 a week later, which will take place either in the lab or online as well. After completing Part 3, participants will then be allowed to complete Part 4 one week later. After completing Part 4 participants will be allowed to complete part 5 one week later. Finally, after completing part 5, participants will then be allowed to continue on to part 6. Each study part will be one week apart.

**16.2 Bulkmail**

Will Texas A&M University bulkmail be used for recruitment?

Yes  No

***Please note that bulkmail recruitment applies to main campus, Health Science Center (HSC), Law School, and Galveston only. Recruitment to the Qatar campus may be require approval by an IRB in Qatar.***

**16.3 How will potential subjects be recruited? Select all that apply:**

- Direct contact in a medical setting
- Direct contact in a non-medical setting
- Newspaper ad
- Television
- Radio
- Website
- Social/professional networking site
- Posted notice(s)
- Letter
- Telephone solicitation
- Email
- Recruiting Pool (See next question)
- Other (specify):

If you selected Recruitment Pools option above, please identify the groups below.

- Economics
- Marketing
- Motor Behavior
- Motor Neuroscience
- Psychology
- Sociology
- TTI

**\* Skip to the next section if using a Recruitment Pool.**

#### 16.4 How will initial contact be made with potential participants?

All contact regarding study participation will take place via the SONA recruitment pool. Participants will choose to sign up for the study after viewing the options for all studies available for research participation credit on SONA. For Part 1, they will be provided with a link to the qualtrics survey. For Parts 2-6, participants will be able to sign up after successfully completing the prior session; however, if they do not successfully complete the writing prompt requirements outlined in Part 1, then they will be unable to continue on to the remaining study sessions (parts 2-6). If this is the case, then the researchers involved in this study will contact participants to let them know their remaining follow-up sessions will be canceled, but will still receive credit for what they have completed.

#### 16.5 How will the researchers protect subject privacy during the recruitment process?

Researchers will protect subject identity during recruitment by adhering to the password protected university SONA system. SONA will grant automatic credit after completion of each part of the study, and any incompletes will be manually granted by the associated researchers after the timeframe for the study is up. This information is protected by SONA and only PIs and research assistants will be able to access information about participation in this study.

#### 16.6 Who will do the recruiting?

SONA systems

#### 16.7 Will recruiting be conducted off Texas A&M University property?

Yes  No

If Yes, describe (Site Authorization(s) may be required.)

#### 16.8 Will screening or recruiting be from or through the patient base of a healthcare provider?

Yes  No

#### 16.9 Do you have any relationship other than as an investigator with participants (e.g. doctor-patient, teacher-student, counselor-student, family member, etc.)?

Yes  No

If Yes, then specify the relationship.

Describe how you will avoid any type of coercion.

By using the SONA system we allow participants to choose from a wide variety of studies and therefore avoid coercion.

#### 16.10 If the subject is a student who is participating in the research for course credit, then how will you ensure that the subject was not coerced into participating?

Psychology professors are required to provide additional options for meeting research participation credit. Furthermore our consent/information forms, which are presented to the subjects before each study session, remind subjects that their participant is entirely voluntary and they are free to withdraw at any time.

#### 16.11 If this study meets a requirement for course research credit, then how is this study suited to the course for which research credit is required?

Since this is a psychological study, students in a psychology course who are receiving course credit for the study will also get the experience of participating in an experiment that hopes to discover more about health psychology, cognitive psychology, and social psychology (all topics that appear in an introduction to psychology course and relate to more advanced psychology courses, such as abnormal or clinical psychology).

**16.12 What alternatives to the participation in the research without negative consequences will you allow (e.g., not to participate, alternative assignment)?**

Participants are welcome to receive research credit by choosing other studies besides ours. They are also given the option of participating in another assignment in which they can write about psychological research instead of participate themselves.

**16.13 Will there be any penalties or other disadvantages for those declining to participate?**

Yes  No

**16.14 Will any pre-screening surveys or questions be used?**

Yes  No

If Yes, then please describe and include in Other Study Documents.

The AUDIT will be used as part of a pre-screening procedure, to increase the rates of alcohol users who complete the study. This measure is already included in the baseline session (and study measures). It is separately included now as a prescreen materials document.

## 17.0 Data Management

**17.1 General Information**

### STANDARD ADMINISTRATIVE PROCEDURE

#### 15.99.03.M1.03 The Responsible Stewardship of Research Data

<http://rules-saps.tamu.edu/PDFs/15.99.03.M1.03.pdf>

Do you agree to adhere to the SAP with your data?

Yes  No

Where will the data be stored? Indicate building and room number on TAMU property.

The data will be collected using the password-secured survey program, Qualtrics. Once data has been collected, it will be saved on TAMU Liberal Arts IT computer server folders associated with the Social-Cognition lab, which are located in the Psychology Building, room 347A. These folders are password protected. The room is also locked and requires a key to enter the office space.

How long will the data be stored? (Note: This time period should be a minimum of 3 years post completion of the research and perhaps longer, depending on sponsor requirements.)

4 years

If you are storing or transmitting collected data, is the storage and transmission of the data encrypted?

Yes  No

Please note that PHI must be stored and transmitted with encryption.

Who will have access to the data?

PI and researchers

## 17.2 Data Safety Monitoring Plan

Yes  No

If so, then:

How is it managed?

With what frequency is data reviewed for this project?

How often does the DSMB meet?

What is the frequency of reports from the DSMB?

Describe any planned interim analysis.

Provide names, affiliations, and qualifications of members.

## 18.0 Informed Consent

### 18.1 Select all that apply and attach to the application:

For templates and guidance regarding informed consent, see <https://rcb.tamu.edu/humans/toolkit/templates/templates>

- Informed Consent Document (signed consent, typically needed in Texas for research involving adults)
- Parent Informed Consent Document
- Parent Permission Form
- Assent Form (typically needed in Texas for research involving children under 18)
- Recruitment Script (verbal)
- Recruitment Email
- Information Sheet (also select Waiver of Documentation of Informed Consent)
- Waiver of Informed Consent
- Waiver of Documentation of Informed Consent
- Other

If other, please specify:

### 18.2 Please provide the readability statistics for each informed consent document in terms of the Flesch-Kincaid Grade Level. In general, informed consent document for adults should be on an 8th grade level.

<https://rcb.tamu.edu/humans/resources/tips-for-writing-consent-forms>

The Information sheet was deemed to be about a 9.0 grade reading level using the Flesch-Kincaid system.

### 18.3 Please describe the informed consent process. Include how participants will be adequately informed of what they will be asked to do in the study as well as how they will be protected. Include how the forms selected above will be used in the process including that the participants will have sufficient time to review any information provided to them.

If a waiver of documentation of informed consent is requested, then the information sheet use must be described here.

After clicking on the Qualtrics link from SONA, participants will be presented with the informed consent form that will provide an overview of what the study is about, who to contact if any questions arise, and other information deemed necessary to give complete informed consent (see attached form). Participants

will be given an option on their computer screen to click "I agree" or "I disagree" to participate in the study. If they agree, then they will continue on and be reminded they are free to discontinue at any time. If they disagree, then they will be taken to an exit screen and prompted to close the browser. Participants will be given as much time as they need to fully read the form as well as email the researchers any questions.

**18.4 Where will the informed consent process take place (e.g. building name, physical address)?**

The informed consent form that participants will either agree to or decline will be housed on the Qualtrics survey program along with other study materials and measures. For all study sessions (Parts 1-6), which are online and can be completed wherever participants see fit, participants will read the consent form wherever they decide to begin the study.

Where will the informed consent documents be physically stored?

See attached consent document (Stored electronically using Qualtrics online survey system that only researchers have the password to).

Who will have access to the Informed Consent documents?

Only the researchers and principal/co-principal investigators.

**18.5 For studies involving research on children, will participants who reach age of majority be consented?**

Yes  No

**18.6 Have the PI, Co-I(s), and any persons interacting with study subjects completed CITI training?**

Yes  No

If No is selected, have the PI, Co-I(s), and any persons interacting with study subjects completed alternative human subjects training? If so, please provide a description and copy of the alternative training.

**18.7 Please indicate the research personnel who will be obtaining informed consent from participants. (Use N/A to indicate that informed consent will not be collected.)**

N/A

**18.8 What project-specific training/experience have individuals obtaining informed consent received (e.g. verbal instruction by the PI, practice with the PI)?**

N/A

**18.9 Will the subject have the opportunity to review the informed consent document or Information Sheet, ask questions, and understand the details of the study prior to participation?**

Yes  No

If Yes, then how much time will be provided?

However much time participants choose to take. Participants first have the opportunity to review the information sheet during Part 1 of the study which is completely online and completed wherever and whenever the participant chooses.

**18.10 How will cultural issues, including language, be addressed?**

Since the study population currently includes only students from an American university, we do not expect any completely non-English speakers to sign up for our study. The information sheet, which is English, asks that participants only click "yes" if they understand what they have read and agree to participation. Our demographics questionnaire does inquire about native language and English fluency. Participants who do not consider themselves fluent in English may be excluded from final analyses since the writing tasks may be influenced by this linguistic issue.

**18.11 Will non-English speaking people be approached to participate in this study?**

Yes  No

Will a translation be available for non-English speaking subjects?

- Verbally (provide script)
- In writing (provide documents)
- Both
- Neither

**18.12 If the study involves minors, then describe the informed consent process of parental permission and how the assent of the minor will be sought. Attach the documents to the application.**

**19.0**

**Waiver of Documentation of Informed Consent**

**19.1 Provide protocol-specific reasons and justification on how *at least one* of the following criteria are met:**

The only record linking the participant and the research would be the consent document, and the principal risk would be potential harm resulting from a breach of confidentiality. Each participant will be asked whether the participant wants documentation linking the participant with the research, and the participant's wishes will govern.

Protocol-specific explanation:

Participants will be given contact information with which they can contact the researchers for a copy of the documentation

That the research presents no more than minimal risk of harm to participants and involves no procedures for which written informed consent is normally required outside of the research context. In cases in which the documentation requirement is waived, the IRB may require the investigator to provide participants with a written statement regarding the research.

Protocol-specific explanation:

Participants will read an information sheet which contains all the elements of informed consent according to 45 CFR§46.116(a). After reading the information sheet, participants will select a box (yes or no) indicating whether they agree to participate in the research. Those who agree to participate will be completing the same measures and procedures as participants recruited via SONA. Participants retain the right to refuse to answer questions which they do not wish to answer.

Official Title of Study: Alcohol PBS and Thinking about the Past

NCT Number: Not Assigned

Unique Protocol ID: IRB20201070D

Date of Document: 09/10/2021

Planned Analysis

[figure not shown]
Statistical Design: The statistical design uses a multilevel structural equation model. The model will compare three conditions: Negative Event, Negative Event w/ a detailed description of the event, Negative Event w/ generated Counterfactuals to reduce future negative events, and Protective Behavioral Strategy Personalized Normative Feedback (PBS-PNF). Each condition will be used to predict protective behavioral strategies. Protective behavioral strategies will then predict alcohol and alcohol consequences. As the conditions are at the between-subject level, the hypotheses are specific to between subject effects, however, the data will be modeled at both the within- and between- subjects level (see Figure 1). In order to decompose variance across levels, all level 1 variables will be centered at the person level while all level 2 variables will be centered at the grandmean. Only weeks during which participants consume alcohol will be included in the analysis, as the intervention target (PBS) only occurs on drinking days.

Covariates: At level 1, we will control for week of study and number of drinking days. At level 2 we will control for biological sex at birth.

Hypothesis 1: Relative to control, the counterfactual condition will result in significantly more use of PBS during drinking days and will be *at least* non-inferior to PBS personalized normative feedback (significant effect of path a).

Hypothesis 2: Relative to control, the counterfactual condition will exert a significant specific indirect effect on alcohol problems through PBS (H2 = path a x path b).

Hypothesis 3: Relative to control, the counterfactual condition will exert a significant total indirect effect on alcohol problems through PBS use and alcohol use ($H3 = H2 + [\text{path a} \times \text{path c} \times \text{path d}]$).

Mplus Code:

usevar are CFcondition PBSPNFcondition NegEventcondition L1PBS L1Drinks
L2PBS L2Drinks Problems;

within are L1PBS L1Drinks;

between are CFcondition PBSPNFcondition NegEventcondition L2PBS L2Drinks;

cluster = ID;

analysis:

estimator = mlr;

PROCESSORS = 2;

type = twolevel;

model:

%within%

L1Drinks on L1PBS;

Problems on L1Drinks L1PBS;

[L1Drinks @0];

[L1PBS @0];

%between%

L2PBS on CFcondition(a);

L2PBS on PBSPNFcondition;

L2PBS on NegEventcondition;

L2Drinks on L2PBS(c);

Problems on L2PBS(b);

Problems on L2Drinks(d);

Model Constraint:

New(H1 H2 H3);

H1 = a;

H2 = a*b

H3 = H2+(c*d);

Exploratory Analysis: We will examine differences between the counterfactual condition and PBS PNF condition to determine equivalence between the two intervention effects. This approach will use a two one-sided equivalence test (TOST), to compare the two active treatments (Lakens, 2017). This allows for a comparison of a new treatment against the observed effects of an existing treatment (rather than against the traditional null hypothesis). In doing so, we will specify an “equivalence” margin of Cohen’s d -0.20 to 0.20 (a small effect in both directions). We will then calculate 95% confidence intervals of the effect size difference between the Counterfactual and PBS-PNF. A positive value indicates a stronger effect of Counterfactual relative to PBS PNF, while a negative value indicates a weaker effect. This approach allows for the statistical determination of whether the observed effect is equivalent to the standard treatment, superior to the standard treatment, or inferior to the standard treatment.

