#### Background

Individuals often think of how a situation or outcome could have turned out differently -- if only something was different or something had changed, then the outcome could have been better or worse. This is a common type of thinking, known as counterfactual thinking, that often takes the form of "if only" statements. These thoughts are frequent after negative events, but have also been found to occur after positive events and 'near misses'. Research has shown that their evaluative nature elicits a variety of consequences, such as biased decision making, changes in an event's meaningfulness, heightened positive or negative affect, and future behavioral changes (such as intentions, motivation, persistence/effort; for review, see: Epstude & Roese, 2008; Roese & Epstude, 2017). Specifically, many areas of research involving counterfactuals have often looked into key elements that are often discussed in other health behavior literature, such as self-efficacy, motivation, and intentions (Tal-Or, Boninger, & Gleicher, 2004; Wong, 2007; Smallman & Roese, 2009). One such area that incorporates these elements is health promotion literature, such as Protective Behavioral Strategies (PBS) and alcohol consumption

(Dvork, Pearson, Neighbors, Martens, & Stevenson, 2016; Dvorak, Pearson, Neighbors, & Martens, 2015). The objectives of this study are laid out as such: First, to further explore the role counterfactuals play in increasing an individual's intentions toward behavioral change. Second, to further elucidate the inner and outer workings of Protective Behavioral Strategies for increasing positive health behaviors. Finally, to address the applicability of a counterfactual intervention on promoting intentions to use PBS.

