## Participants

Participants will be recruited via the Texas A&M University online research subject pool (SONA). To be included in the study procedures and subsequent data analyses, participants must be 18 or older and complete all parts. There are no exclusion criteria for participation in the baseline study (part 1). However, participants who do not follow the instructions for the specific writing task will be unable to sign-up for the remaining follow up sessions (Parts 2-6) and will be excluded from the final data analyses. For Part 1, they will be provided with a link to the Qualtrics survey (if completing online) or will sign up via SONA for an in-person lab session. For Parts 2-5, participants will be able to sign up after successfully completing the prior session; however, if they do not successfully complete the writing prompt requirements outlined in Part 1, then they will be unable to continue on to the remaining study sessions (parts 2-6). If this is the case, then the researchers involved in this study will contact participants to let them know their remaining follow-up sessions will be canceled, but will still receive credit for what they have completed.

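### The model lets condition reach alcohol problems only through PBS, so no direct or total effect on problems is estimated, and the coded H3 drops path a

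*SAP*

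**What the plan says.** Under Statistical Design the SAP sets out a chain: "Each condition will be used to predict protective behavioral strategies. Protective behavioral strategies will then predict alcohol and alcohol consequences". Hypothesis 1 is path a, condition to PBS. Hypothesis 2 is the specific indirect effect a × b on problems. Hypothesis 3 is described as a "total indirect effect on alcohol problems through PBS use and alcohol use", defined in the text as H2 + a × c × d.

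At the between level of the Mplus code, the three arm indicators (counterfactual, PBS-PNF, negative event) predict only L2PBS. Drinks have one predictor, in the line beginning "L2Drinks on L2PBS(c". Problems have two, PBS in the line beginning "Problems on L2PBS(b" and drinks (path d). Model Constraint creates H1, H2 and H3 and nothing else, and there H3 is H2 + c × d.

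The only other planned contrast is the exploratory equivalence test of counterfactual against PBS-PNF. It does not involve control and names no outcome. The protocol has no analysis section that adds a comparison.

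Two restrictions bear on any comparison of problems. The SAP says "Only weeks during which participants consume alcohol will be included in the analysis". Protocol 8.1, Participants, says that for inclusion in procedures and analyses "participants must be 18 or older and complete all parts".

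**The concern.** Leaving condition out of the equations for drinks and problems fixes both paths at zero. Within such a model, text H3 equals the total effect on problems by construction. If condition also acts by another route, the two differ and nothing in the planned output shows it. The contrast that randomisation protects, problems by arm, is never estimated. H2 and H3 depend on b, c and d, which are associations between post-randomisation variables.

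An overall reading is easy to slip into. Two of the three hypotheses name alcohol problems, the SAP describes the arm as "Negative Event w/ generated Counterfactuals to reduce future negative events", and protocol 12.3 looks ahead to strategies for treating binge drinking. Protocol 8.1, Significance, lists both helpful and unhelpful consequences of counterfactual thinking. That either kind could affect problems outside PBS is an inference, but it means a direct effect could have either sign.

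The coded H3 is a more definite fault. It contradicts the text formula, and its second term does not involve condition.

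**Working it through.** **Structure.** Of the four labelled between-level paths (a, b, c, d), only a starts at condition, and it ends at PBS. Write e for condition to drinks and f for condition to problems; the plan sets both to zero. Then:

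- direct effect = f
- effect outside PBS = f + e × d
- text H3 = a × b + a × c × d
- total effect = f + e × d + a × b + a × c × d

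Text H3 equals the total only if f + e × d = 0.

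**Assumed inputs.** The documents give no effect sizes or SDs, and protocol 9.1 gives 1500 without a power calculation. For illustration: a = 0.3, b = -0.2, c = -0.3, d = 0.4, four equal arms, SD of problems about 1.

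- Text H3 = 0.3 × (-0.2) + 0.3 × (-0.3) × 0.4 = -0.060 - 0.036 = -0.096.
- Coded H3 = -0.060 + (-0.3) × 0.4 = -0.180.
- With a = 0: text H3 = 0, coded H3 = -0.120.

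**Simulation** (between level only, complete data, delta-method intervals, 3000 trials per setting, e = 0). Entries are percentages of trials whose 95% interval excludes zero.

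| f | True total (SD) | N = 800: text H3 benefit | N = 800: total benefit / harm | N = 1500: text H3 benefit | N = 1500: total benefit / harm |
|---|---|---|---|---|---|
| -0.25 | -0.35 | 84.6 | 94 / 0 | 98.3 | 99.7 / 0 |
| -0.10 | -0.20 | 84.6 | 50 / 0 | 98.3 | 76 / 0 |
| 0 | -0.10 | 84.6 | 16 / 0.1 | 98.3 | 25 / 0.1 |
| +0.10 | 0.00 | 84.6 | 2 / 2 | 98.3 | 2 / 2.5 |
| +0.25 | +0.15 | 84.6 | 0 / 34 | 98.3 | 0 / 57 |

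The H3 figures are the same with the extra paths fixed or freed. The mismatch runs both ways: at f = -0.25, H3 averages -0.10 against a total of -0.35. Routing the extra effect through drinking (e = -0.25 or +0.25, N = 800) gives totals of -0.20 and 0.00, with H3 benefit again 84.6% in both.

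Under weaker assumptions at N = 800, H3 benefit is 50% with a = 0.2, 83% with b halved, and 64–69% with b, c and d all halved.

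**Coded H3 when a = 0 and there is no direct effect.** It shows apparent benefit in 87–88%, about 99% and 100% of trials at N = 400, 800 and 1500, against 2–3% for the text formula.

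**Precision of the total effect.** Half-width = 1.96 × √(2/n per arm). With 100, 200 and 375 per arm this is 0.28, 0.20 and 0.14 SD.

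**Drinking weeks.** Suppose 1.0 problem per drinking week in both arms, with 50% drinking weeks in one arm and 60% in the other. The all-weeks means are 0.50 and 0.60, a difference of -17%, while the drinking-weeks contrast is 0.

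**The case against.** The strongest reply is that the SAP promises mediation and delivers it. H2 and H3 are labelled as indirect effects, and neither claims an overall effect. The objectives in protocol 8.1, Background, concern intentions and PBS, ending with the aim "to address the applicability of a counterfactual intervention on promoting intentions to use PBS". This stands. A reader might infer that the fixed paths invalidate H2 and H3, but the working does not support that. At N = 800, mean b moves only from -0.200 (freed) to -0.214 or -0.186 (fixed) at f = -0.25 or +0.25, and the significance of H3 is unchanged.

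A reader might also infer that the intervention is likely to have a harmful direct effect, or that the percentages above forecast this trial. Neither follows. A direct effect of ±0.25 is about 2.6 times the assumed indirect effect (0.25/0.096), and nothing in the documents supports that size. Only 1500 is a documented sample size. Equality of the total with the raw arm contrast was checked for a between-level model with complete data, not for the planned two-level model with unequal numbers of drinking weeks.

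Finally, the code omits covariates that the SAP lists and Figure 1 could not be seen. What can be said with confidence is that the paths are absent from the prose and code, not that nobody planned them.

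The reply does not reach the coded H3, which disagrees with the SAP's own formula whatever the coefficients.

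**Conclusion.** The point holds in a limited form. As written in prose and code, the plan imposes full mediation through PBS without testing it, and it estimates neither a direct nor a total effect of the counterfactual arm on alcohol problems against control. H2 and text H3 stand as effects through PBS. They cannot support a statement that problems fell or rose overall, because they look much the same whether the total effect is beneficial, null or harmful. The sizes shown are illustrative and rest wholly on assumed coefficients. The structural statement needs no such assumption but is subject to Figure 1.

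The coded H3 is wrong as written: it omits path a and can be significant when condition has no effect on PBS.

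This should be fixed before analysis. It does not undermine the PBS-route hypotheses once H3 is coded as stated.

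**What to change.** 1. In Model Constraint, code `H2 = a*b;` (the semicolon is missing) and `H3 = H2 + (a*c*d);`.
2. At the between level, regress both L2Drinks and Problems on all three arm indicators, labelling the counterfactual paths e and f. Define direct = f, outside PBS = f + e*d, and total = outside PBS + H3. Report all three with 95% confidence intervals beside H2 and H3, as estimates and not as a gate.
3. Word conclusions from H2 and H3 as effects through PBS, and rest any overall statement about problems on the total effect.
4. Have the investigators confirm which arm is control. The SAP does not define it; the indicator left out of the code implies fact listing.
5. Confirm how problems are measured after baseline. The protocol's task list has the YAACQ only before the manipulation; the list of situations in the weekly follow-up may be another source. If there is follow-up measurement, also report the arm difference over all weeks for all randomised participants with follow-up data. State that this is still a post-randomisation subset: those who fail the writing task are barred from Parts 2–6 (protocol 8.1, Participants, and 9.4), and the tasks differ by arm. Report those exclusions by arm.
6. If Figure 1 already shows the added paths, bring the prose and code into line with it.

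The cost is two corrected lines, six parameters, three derived quantities and one extra comparison. No new data are needed if problems are collected at follow-up; if they are not, H2 and H3 lack an outcome too, which is a prior problem. The downside is imprecision. With the assumed coefficients and no direct effect, the total-effect test has 10%, 16% and 25% power at N = 400, 800 and 1500, and the estimate has the wrong sign in 25%, 16% and 9% of trials. The direct and outside-PBS effects also rest on non-randomised paths, and the model-based total keeps the drinking-weeks and completer restrictions.
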